### 3. STUDY DESIGN

#### 3.1 Study Design

This 3-part study has been approved by the Paediatric Committee of the European Medicines Agency as part of the Paediatric Investigational Plan for lanthanum carbonate. Pharmacokinetic data will be collected during the study as there are currently no data on lanthanum carbonate in pediatric patients under the age of 18 years. The data from this study will be evaluated against historical systemic exposure data in adults. The pharmacokinetic assessment is combined with the efficacy and safety sections to reduce the number of studies to be performed and to ease subject enrollment.

##### Part 1: Single-dose, pharmacokinetic assessment

This part of the study was a single-dose pharmacokinetic assessment of lanthanum carbonate in at least 8 subjects. There was a 2-week screening period during which eligibility was determined for Part 1. Subjects who were eligible to participate entered a washout period of up to 3 weeks if the phosphorus level was not above KDOQI required levels. During the washout period the existing phosphate binder treatment was discontinued until phosphate levels had risen above 6.0mg/dL (1.94mmol/L) in subjects aged under 12 years or >5.5mg/dL (1.78mmol/L) in subjects aged over 12 years. At the end of the washout period, subjects were assessed for inclusion in the study based on their serum phosphorus levels.

Subjects participating in Part 1 could begin Part 2a immediately following the completion of the pharmacokinetic assessments. Subjects not participating in Part 1 entered Part 2a after screening at Visit 2/Week 0 (see [Table 1](#)).

Part 1 is complete and an interim clinical study report interpreting and summarizing the data is available.

##### Part 2a: Open-label, active comparator crossover period

Originally, the design of Part 2 of Study SPD405-207 was a crossover non-inferiority one to allow a formal comparison of the efficacy of lanthanum carbonate with calcium carbonate. It was a single-sequence design (8 weeks of calcium carbonate followed by 8 weeks of lanthanum carbonate) to minimize disruption to the subjects. The comparator calcium carbonate was selected to meet the comparator criteria outlined by Pediatric Committee of the European Medicines Agency. Since the originally proposed study included only 1 sequence (calcium carbonate for the 1st treatment period and lanthanum carbonate for the 2nd treatment period) blinding was not applicable, thus the study was open-label. As shown in the study schematic in [Figure 1](#), all subjects were to receive lanthanum carbonate in period 2 of the crossover and had the option to continue on to Part 3 of the study on the same treatment for up to 6 months. If needed, there was a washout period for up to 3 weeks between treatment with calcium carbonate (Treatment Period 1) and lanthanum carbonate (Treatment Period 2). Subjects who discontinued calcium carbonate treatment period/Treatment Period 1 due to hypercalcemia in Part 2 of the

originally proposed study could also continue to Part 3 to receive lanthanum carbonate treatment (see Section 4.4.1 and Section 6.2.1 [Dosing, Hypercalcemia]) for up to 6 additional months.

No new subject will be enrolled in Part 2a under Version 6.0 of the protocol.

#### Part 2b: 8-week lanthanum carbonate treatment

[figure not shown]
Given the extreme difficulty in recruiting enough subjects to obtain the originally proposed sample size of 50 subjects required for the Per-protocol Set for a cross-over non-inferiority study, the active comparator (calcium carbonate) treatment arm was removed (see Part 2a) in Part 2b; serious consideration had to be given to adjust the sample size and focus of the study to safety, in order to complete it. The sample size has been adjusted to include at least 35 subjects who will complete 8 weeks of treatment with lanthanum carbonate and will be assessable for the primary endpoint. As shown in the study schematic in Figure 2, eligible subjects will be enrolled in Part 2b after screening at Visit 1/Week 0 (see Table 3) to receive 8 weeks of lanthanum carbonate treatment only under Version 6.0 of the protocol. Subjects in Part 2b will have the option to continue on to Part 3 of the study on the same treatment for up to 6 additional months.

#### Part 3: 6-month lanthanum carbonate treatment

Subjects in Part 2a (including subjects in Treatment Period 1/calcium carbonate treatment arm who discontinued due to hypercalcemia; see Section 4.4.1 and Section 6.2.1 [Dosing, Hypercalcemia]) and Part 2b may continue to receive open-label lanthanum carbonate for up to 6 additional months of therapy.

The doses selected for Part 1 of the study were those that were suggested for use in children in clinical practice and those in Part 2 are based on known phosphate binder values for maintaining phosphate level balance.

**Figure 1: Study Design Flow Chart- Part 1, Part 2a (Treatment Periods 1 and 2) and Part 3**

[figure not shown]

\* Screening is only required once, either at Part 1 for subjects participating, otherwise at Part 2.

\*\* The washout is only required if phosphorus is below KDOQI guidelines.

Note: The schematic in Figure 1 is applicable to the originally proposed open-label cross over study design.

**Figure 2: Study Design Flow Chart- Part 2b and Part 3**

\*Eligible subjects will enter Part 2b to receive 8 weeks of lanthanum carbonate treatment only under Version 6.0 of the protocol. Screening will occur at Visit 1, Week 0. The washout (W1) is only required if phosphorus is below KDOQI guidelines.

### 3.2 Number and Type of Subjects

Children and adolescents aged 10 years to <18 years with CKD who are on dialysis, will be eligible to participate, providing they are on solid food.

Subjects were recruited to provide at least 8 evaluable subjects in Part 1 (single-dose pharmacokinetic assessment). After completing participation in Part 1, subjects entered Part 2a (short-term efficacy and safety assessments). Part 1 of the study is complete. No new subject will enroll in Part 2a under Version 6.0 of the protocol.

The study is planned to enroll at least 35 subjects who complete 8 weeks of treatment with lanthanum carbonate and are assessable for the primary endpoint. Approximately 65 subjects may be enrolled to achieve this target. Under Version 6.0 of the protocol, all new subjects will be enrolled in Part 2b (modified Part 2a) and will be treated with lanthanum carbonate only (see Section 3.1).

### 3.3 Investigational Product

Lanthanum carbonate oral powder packaged in 250mg sachets will be administered following breakfast in Part 1. In Parts 2a, 2b, and 3, the lanthanum carbonate powder will be mixed with soft food, the total daily dose being divided between meals and titrated as appropriate to achieve or maintain serum phosphate levels in accordance with KDOQI age guidelines or until a maximum daily dose of 3000mg is reached.

Calcium carbonate (500mg tablets) was orally administered either alone or mixed with food, and dosing was based on standard clinical practice in order to achieve or maintain serum phosphorus levels in accordance with KDOQI age guidelines. Calcium carbonate was administered during

Part 2a only (see [Table 1](#)). Under Version 6.0 of the protocol, only lanthanum carbonate will be administered for 8 weeks of treatment in Part 2b (see [Table 3](#)).

### 3.4 Sites and Regions

Up to 36 sites are expected to participate in this study, from European Union, Russian Federation, and Republic of Turkey.

## 4. STUDY POPULATION

### 4.1 Inclusion Criteria

The subject cannot be enrolled in the study before all of the following inclusion criteria (including test results) are met.

1. Aged 10 years to <18 years of age at the time of consent.
2. Subject or parent/legally authorized representative (LAR) understand and are able, willing, and likely to fully comply with the study procedures and restrictions defined in this protocol.
3. Male, or non-pregnant, non-lactating female who agrees to comply with any applicable contraceptive requirements of the protocol.
4. Established CKD, on dialysis, and requires treatment for hyperphosphatemia with a phosphate binder.
5. Serum phosphorus levels after a washout period of up to 3 weeks as follows:
  - Age <12 years: Serum phosphorus >6.0mg/dL (1.94mmol/L)
  - Age 12 years and older: Serum phosphorus >5.5mg/dL (1.78mmol/L)
6. Ability to provide written, signed and dated (personally or via an LAR) informed consent/and assent, as applicable, to participate in the study.

### 4.2 Exclusion Criteria

Subjects are excluded from the study if any of the following exclusion criteria are met.

1. Current or recurrent disease (eg, cardiovascular, liver, unstable and uncontrolled gastrointestinal, malignancy, or other conditions) other than CKD or end-stage renal disease that could affect the action, absorption or disposition of the investigational product, or clinical or laboratory assessments.
2. Current or relevant history of physical or psychiatric illness, any medical disorder (except for CKD or end-stage renal disease and related co-morbidities) that may require treatment or make the subject unlikely to fully complete the study, or any condition that presents undue risk from the investigational product or procedures.
3. Unable to eat semi-solid foods or on Total Enteral Alimentation.
4. Known or suspected intolerance or hypersensitivity to the investigational product(s), closely related compounds, or any of the stated ingredients.

5. History of alcohol or other substance abuse within the last year.
6. Current use of any medication (including over-the-counter, herbal, or homeopathic preparations) that could affect (improve or worsen) the condition being studied, or could affect the action, absorption, or disposition of the investigational product(s), or clinical or laboratory assessment.
7. Weight and age of subject are outside of local applicable criteria for blood sample volume limits.
8. Use of another investigational product within 30 days prior to receiving the first dose of investigational product.

### **4.3 Reproductive Potential**

All females must have a negative serum beta human chorionic gonadotropin pregnancy test at Visit 1.0 and/or Visit 2.0. Females must abstain from sexual activity that could result in pregnancy or agree to use acceptable methods of contraception.

Condoms should be used with the following acceptable contraceptives:

- Intrauterine devices
- Hormonal contraceptives (oral, depot, patch, injectable, or vaginal ring).

Other acceptable contraception methods are:

- Double barrier methods (eg, condoms and diaphragms with spermicidal gel or foam).

Sexually active females should have been using an acceptable form of contraception for at least 4 weeks prior to enrollment. All females must be advised to use acceptable contraceptives throughout the study period and for 30 days following the last dose of investigational product. If hormonal contraceptives are used they should be administered according to the package insert. Females who are not currently sexually active must agree to use acceptable contraception, as defined above, if they become sexually active during the period of the study and 30 days following the last dose of investigational product.

#### **4.3.1 Restrictions**

None.

### **4.4 Withdrawal of Subjects**

A subject may withdraw from the study at any time for any reason without prejudice to their future medical care by the physician or at the institution. The Investigator or Sponsor may withdraw the subject at any time (eg, in the interest of subject safety). The withdrawal of a subject from investigational product by the Investigator should be discussed where possible with the Medical Monitor before the subject stops investigational product.

If investigational product is permanently discontinued, regardless of the reason, the final evaluations are to be performed as completely as possible. Whenever possible, all discontinued subjects should also undergo the protocol-specified follow-up. Comments (spontaneous or

elicited) or complaints made by the subject must be recorded in the source documents. The reason for termination, date of stopping investigational product, and the total amount of investigational product taken must be recorded on the case report form (CRF) and source documents.

#### 4.4.1 Subject Stopping Criteria

Subjects must be removed from study if any 1 or more of the following events occur:

- Violation of inclusion/exclusion criteria at study entry
- Taking another non-study phosphate binder (on either calcium carbonate and lanthanum carbonate arms) rather than the investigational product during the study
- Kidney transplant during the study. Subjects should be followed 30±7 days post-transplant
- Pregnancy
- Serum phosphorus rises above 10.0mg/dL (3.23mmol/L) during the study (however this does not apply during the washout periods)
- Calcium level rises to >11.5mg/dL (2.88mmol/L) during the first treatment period of Part 2a (calcium carbonate). Subjects may continue to Part 3 but must complete all procedures for Visit 2.4 prior to commencing Part 3.

See [APPENDIX 2](#) for guidelines on phosphorus and calcium levels.

#### 4.4.2 Reasons for Discontinuation

The reason for withdrawal must be determined by the Investigator and recorded in the subject's medical record and on the CRF. If a subject is withdrawn for more than 1 reason, each reason should be documented in the source document and the most clinically relevant reason should be entered on the CRF.

If an adverse event (AE) is a reason for discontinuation, then "adverse event" must be recorded as the reason for discontinuation on the CRF.

Reasons for discontinuation include but are not limited to:

- Death
- Withdrawal by subject
- Lost to follow-up
- Lack of efficacy
- Physician decision
- Pregnancy
- Kidney transplant
- Other (must be specified. eg, met stopping 1 or more stopping criteria).

Reasons for possible discontinuation (to be determined by Sponsor and Investigator discussion) include but are not limited to:

- Adverse event
- Protocol violation
- Non-compliance with study drug
- Progressive disease.

#### 4.4.3 Subjects ‘Lost to Follow-up’ Prior to Last Scheduled Visit

At least 3 documented attempts must be made to contact any subject lost to follow-up at any time point prior to the last scheduled contact (office visit or telephone contact). One of these documented attempts must include a written communication sent to the subject’s last known address via courier or mail (with an acknowledgement of receipt request) asking that they return any unused investigational product and return to the site for final safety evaluations.

### 5. PRIOR AND CONCOMITANT TREATMENT

#### 5.1 Prior Treatment

Prior treatment includes all treatment (including over-the-counter, herbal treatments, vitamins, non-pharmacological treatment such as psychotherapy as appropriate), received within 30 days of, and discontinued prior to, the date of first dose of investigational product. Prior treatment information must be recorded on the appropriate CRF page.

Subjects taking growth hormone must have started their treatment at least 2 months prior to Visit 1.0 (Part 1, [Table 1](#) or Part 2b and 3, [Table 3](#)) or Visit 2.0 (Part 2a and 3, [Table 1](#)).

Treatment with proton pump inhibitors must be initiated at least 4 weeks prior to Visit 1.0 (Part 1, [Table 1](#) or Part 2b and 3, [Table 3](#)) or Visit 2.0 (Part 2a and 3, [Table 1](#)).

[Table 4](#) details the washout period for common prior treatments and highlights excluded medications.

**Table 4: Common Excluded Treatments and Washout Period**

Treatment	Washout	Examples (if applicable)
Cinacalcet hydrochloride	Up to 3 weeks a	MIMPARA
Sevelamer hydrochloride	Up to 3 weeks a	RENAGEL, RENVELA

a Until phosphate levels are <6.0mg/dL (1.94mmol/L) for subjects under 12 years or <5.5mg/dL (1.78mmol/L) for subjects aged 12 years and over

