**Screening:**

There will be a 2-week screening period during which eligibility will be determined. Subjects who are eligible to participate will enter a washout period of up to 3 weeks if the phosphorus level is not above KDOQI required levels. During the washout period the existing phosphate binder treatment will be discontinued until phosphate levels have risen above 6.0mg/dL (1.94mmol/L) in subjects aged under 12 years or >5.5mg/dL (1.78mmol/L) in subjects aged over 12 years. At the end of the washout period, subjects will be assessed for inclusion in the study based on their serum phosphorus levels.

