##### **Part 2a (between Visits 2.0 and 2.1) and Part 2b (between Visit 1.0 and 2.1)**

Subjects must stop taking any phosphate binder medication for up to 3 weeks prior to the first dose of investigational product if their phosphate levels are <6.0mg/dL (1.94mmol/L) for subjects under 12 years or <5.5mg/dL (1.78mmol/L) for subjects aged 12 years and over.

If a subject aged under 12 years already has phosphate levels >6.0mg/dL (1.94mmol/L) or >5.5mg/dL (1.78mmol/L) for subjects aged 12 years and older, the subject may proceed directly to the next part of the study (Visit 2.1). If a subject has started calcium carbonate or lanthanum carbonate based on local laboratory results, the subject will be allowed to continue in the study even if central laboratory results do not agree.

If phosphate levels reach >6.0mg/dL (1.94mmol/L) for subjects aged under 12 years or >5.5mg/dL (1.78mmol/L) for subjects aged 12 years and older during the washout, the subject will be withdrawn from washout and start the next part of the study (Visit 2.1).

Blood sample(s) will be taken locally during the washout period to ensure the phosphorus reaches the KDOQI required level. When reached, the phosphate level should be confirmed by taking a sample (between 0.1-0.7mL depending on each country's specific requirements) which will be analyzed by the central laboratory. However subjects can be enrolled based on the local laboratory result.

Any AEs or changes to concomitant medication will be recorded.

Subjects who have participated in Part 1 do not need to have a washout prior to entering Part 2 (not applicable to part 2b).

Subjects who have completed the washout (W1) and have phosphate levels equal to or greater than the age appropriate KDOQI guidance (serum phosphorus >6.0mg/dL [1.94mmol/L] for subjects aged under 12 years; >5.5mg/dL [1.78mmol/L] for subjects aged 12 years and older) will:

- Part 2a: Be dispensed calcium carbonate at either the dose taken by the subject prior to starting the study or at a dose determined by the Investigator for new subjects based on standard clinical practice.
- Part 2b: Be dispensed lanthanum carbonate with the starting total daily dose as 1500mg for all subjects. The total daily dose will be titrated 2-weekly, as appropriate, until the target serum phosphorus level is achieved, or until a maximum daily dose of 3000mg is reached.
- Have any AEs that occurred since the last visit recorded.

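### Protocol Table 4 footnote a ends the prior-treatment washout below the phosphate limit; the screening and W1 text end it above, and inclusion criterion 5 requires a value above

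*Protocol*

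**What the plan says.** Protocol Section 5.1 states that Table 4 "details the washout period for common prior treatments and highlights excluded medications". Table 4 has two rows, cinacalcet hydrochloride and sevelamer hydrochloride. Each has a washout of up to 3 weeks with footnote a: "Until phosphate levels are <6.0mg/dL (1.94mmol/L) for subjects under 12 years or <5.5mg/dL (1.78mmol/L) for subjects aged 12 years and over".

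Other current text on the same washout reads as follows.

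- Synopsis, Screening: "the existing phosphate binder treatment will be discontinued until phosphate levels have risen above 6.0mg/dL (1.94mmol/L" for subjects under 12, with a limit of >5.5 mg/dL for older subjects.
- Section 7.1.1.4, Washout (W1), Parts 2a and 2b, start: subjects must stop any phosphate binder "if their phosphate levels are <6.0mg/dL (1.94mmol/L) for subjects under 12 years or <5.5mg/dL (1.78mmol/L) for subjects aged 12 years and over".
- Same section, already above the limit: "the subject may proceed directly to the next part of the study (Visit 2.1".
- Same section, end, after the matching >6.0 mg/dL limit for subjects under 12: ">5.5mg/dL (1.78mmol/L) for subjects aged 12 years and older during the washout, the subject will be withdrawn from washout".
- Section 4.1, criterion 5, assessed after the washout: "Age 12 years and older: Serum phosphorus >5.5mg/dL (1.78mmol/L", and >6.0 mg/dL under 12 years.
- Section 4.1, opening sentence: "The subject cannot be enrolled in the study before all of the following inclusion criteria (including test results) are met".

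**The concern.** The footnote is a decision threshold in operative text, placed in the table that Section 5.1 names for these two drugs. Its inequality points the opposite way from the washout instructions and the entry criterion. The values it gives as the point at which washout stops are the values that Section 7.1.1.4 gives as the reason to start it; the footnote has *until* where Section 7.1.1.4 has *if*. A site that relies on Table 4 alone would therefore work to the reverse of the rule in the visit-level text. What is at stake is whether, and for how long, a child on one of these drugs is washed out before study drug starts.

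**Working it through.** The plan gives no figure to reproduce. The check compares the inequality signs, after confirming that the limits themselves agree.

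**Units.** Appendix 2 pairs 10.0 mg/dL with 3.23 mmol/L, a factor of 3.23 / 10.0 = 0.323. Then 6.0 × 0.323 = 1.94 and 5.5 × 0.323 = 1.78 mmol/L. The limits match everywhere, so only the direction differs.

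**Conditions side by side** (P = serum phosphate, mg/dL)

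| Source | Role of the condition | Under 12 years | 12 years and over |
|---|---|---|---|
| Table 4, footnote a | end of washout | P < 6.0 | P < 5.5 |
| Section 7.1.1.4 (W1) | start of washout | P < 6.0 | P < 5.5 |
| Section 7.1.1.4 (W1) | end of washout | P > 6.0 | P > 5.5 |
| Synopsis, Screening | end of washout | P > 6.0 | P > 5.5 |
| Section 4.1, criterion 5 | entry, after washout | P > 6.0 | P > 5.5 |

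In each age group the first row and the last three rows are disjoint. A value exactly at the limit meets neither strict inequality. No phosphate value can satisfy both.

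**Scope by study part.** Section 3.1 says that Part 1 is complete and that Part 2a takes no new subjects. The live conflict is for new Part 2b subjects.

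**Scope by drug.** Section 2.1 names sevelamer among the calcium-free phosphate binders, so the synopsis and W1 text apply to it directly and the footnote conflicts with both, as well as with criterion 5. Section 5.2 lists cinacalcet apart from compounds used as binders. The synopsis text and the W1 start sentence speak of phosphate binders, while the W1 sentences on proceeding and on leaving washout name no drug. Whether they reach cinacalcet is unclear. Criterion 5 applies after washout whatever drug was washed out, so for cinacalcet that conflict is the certain one.

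**Literal effect, sevelamer only.** The cap is 3 weeks × 7 = 21 days.

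- Below the limit on day 0: the footnote's end condition is already met, so washout is 0 days, against up to 21 days under W1. The subject cannot meet criterion 5 on that value.
- Above the limit on day 0: W1 permits the subject to proceed, so 0 days. The footnote's end condition is not met, so the wait could reach the cap, up to 21 − 0 = 21 days.

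**The case against.** The strongest reply is that this is a recognisable drafting slip with little practical reach. The footnote repeats the W1 start condition with one word changed, and every procedural passage for Part 2b runs upward. Section 6.2.1 and Section 7.1.1.3 put an otherwise eligible subject whose phosphate is too low into W1. Section 7.1.1.4 tells such a subject to stop any binder, and Section 4.1 bars enrolment until criterion 5 is met. Some of these passages pair wording that includes equality with a strict > sign, but that concerns the boundary value only and the direction stays upward.

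Most of this stands. It makes the 0-day and 21-day outcomes theoretical, since a site would have to follow the footnote and disregard several direct instructions. It does not remove the contradiction. None of those passages amends Table 4, the SAP does not correct it, and nothing says which text prevails.

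A reader might infer more: that ineligible subjects would be enrolled, or that the primary result would be distorted. The documents do not support this. Section 4.1 blocks such an enrolment, and no definition of the endpoint, analysis sets or sample size uses Table 4. A reader might also apply the 21-day contrasts to cinacalcet. They are measured against text that may not cover that drug, so they are confined to sevelamer here.

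**Conclusion.** The contradiction is real and is in current text: the footnote's end condition and those of the synopsis and W1 text cannot both be met, and a value that meets the footnote fails criterion 5. It concerns new Part 2b subjects taking sevelamer or cinacalcet, whose number the documents do not give. For sevelamer the literal difference is at most 21 days in either direction, and the protocol's other instructions make that ceiling unlikely to be reached. Practical severity is low. It still merits correction, because a reversed threshold should not be left for sites to resolve by judgement. The conclusion rests on reading *until* in the footnote as the end condition of the washout. It takes no position on which clinical rule is right.

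**What to change.** Reconcile Table 4 footnote a with the synopsis screening text, Section 4.1 criterion 5, Section 7.1.1.3 and Section 7.1.1.4, so that one direction of the threshold governs the end of the prior-treatment washout. State explicitly whether that rule applies to cinacalcet. Notify sites of the reconciled text. The sponsor decides the clinical rule. The cost is a one-line protocol correction or a clarification letter, with no change to any analysis.
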